3 STATISTICAL METHODS

3.1 General Principles

- All hypothesis testing will be performed using a two-sided test at a 0.05 level of significance or a one-sided test at a 0.025 level of significance. Significance levels will be adjusted for multiple hypothesis testing where appropriate. P-values will be reported as raw uncorrected p-values and rounded to three decimal places. If a p-value is less than 0.001 it will be reported as “< 0.001.”
- Summary statistics will be reported for all analyzed variables.
 - Continuous data will be summarized using descriptive statistics appropriate for the underlying data distribution, e.g., mean, standard deviation, median, and interquartile range (first and third quartiles).
 - Categorical, non-ordered variables will be summarized using frequency counts and percentages.
 - Ordinal variables, including those specific to study outcomes – e.g., the modified Movement Disorder Society Unified Parkinson’s Disease Rating Scale (MDS-UPDRS) Part III and the Bain & Findley Activities of Daily Living (BF-ADL) scale – will be summarized using measures of central tendency and variance as opposed to frequency counts and percentages; that is, these variables will be reported using the same metrics as defined above for continuous variables.
- For events which can occur more than once in a single subject (e.g., adverse events), the percentage will be based on number of subjects experiencing the event, and both subject and event counts will be reported.
- Baseline is defined as the last measurement for the outcome of interest obtained before the exposure to study treatment.
- For time-to-event analyses, complete dates for events of interest (e.g., index treatment, outcome events, censoring), will always be used. Incomplete dates will be incorporated by defining the event as occurring on the earliest date possible given the incomplete information. E.g., a date of UNK-FEB-2018 will be incorporated into the analysis as 01-FEB-2018.
- Statistical analyses will be performed in SAS (SAS Institute, Cary, N.C.) version 9.3 or later, R (R Foundation for Statistical Computing, Vienna, Austria) version 3.2 or later,

Matlab (The MathWorks, Inc., Natick, MA) version R2016B or later, Python (Anaconda, Inc., Austin, TX) version 3.6.6 or later, or in another validated statistical software package.

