3.4 Secondary Endpoints

The study’s secondary endpoints reflect within-subject acute and longitudinal improvements of MDS-UPDRS score from tasks specific to action tremor and BF-ADL score from pre-stimulation to post-stimulation at Visits 2b and 3, captured as defined in the protocol. The statistical objective of the secondary endpoint is to demonstrate, using clinician-rated and patient rated measures, that action hand tremor severity in PD is reduced after treatment with the Cala Trio device.

For purposes of the secondary endpoint:

- ***MDS-UPDRS score*** is defined as the ***average of UPDRS ratings from the two assessed action tremor tasks (postural hold and kinetic) relevant to the stimulated upper limb.***
Observations where either of these two assessments are missing will not be included in the analysis set.

- **BF-ADL score** is defined as the *average of available BF-ADL ratings from the eight assessed tasks (use a spoon to drink soup, hold a cup of tea, pour milk from a bottle or carton, dial a telephone, pick up your change in a shop, insert an electric plug into a socket, unlock your front door with the key, write a letter) relevant to the stimulated upper limb*. For observations where ratings for a subset of these tasks are missing, the BF-ADL ratings from the remaining tasks will be averaged and the observation will still be eligible for inclusion in the analysis set. This was done because missing data are assumed to result from participants not having the necessary props readily available (i.e., data are “missing at random”) and not because participants were systematically unable to perform the respective ADL task.

The secondary endpoints are:

- 1a. Improvement in the MDS-UPDRS score from pre-stimulation to post-stimulation at Visit 2b.
- 1b. Improvement in the MDS-UPDRS score from pre-stimulation to post-stimulation at Visit 3.
- 1c. Improvement in BF-ADL score from pre-stimulation to post-stimulation at Visit 2b.
- 1d. Improvement in BF-ADL score from pre-stimulation to post-stimulation at Visit 3.
- 2a. Improvement in the MDS-UPDRS score from Visit 2b pre-stimulation to Visit 3 post-stimulation.
- 2b. Improvement in BF-ADL score from Visit 2b pre-stimulation to Visit 3 post-stimulation.
- 3a. Improvement in the MDS-UPDRS score from Visit 2b pre-stimulation to Visit 3 pre-stimulation.
- 3b. Improvement in BF-ADL score from Visit 2b pre-stimulation to Visit 3 pre-stimulation.

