3.10 Subgroup and Covariate Analysis

Primary and secondary endpoints will be investigated for each of the following subgroups:

- Gender (M/F)
- Age (< 65 vs. \geq 65 years)
- Age onset of hand tremor in PD (by median split)
- Duration of PD from beginning of tremor symptom (by median split)
- Tremor Medications (On/Off)
- Antidepressant medications (On/Off)
- Preset Stimulation amplitude (by median split)
- Average Final Stimulation amplitude (by median/mean split)
- Stimulation calibration frequency (by median split)
- Baseline tremor severity as measured by UPDRS (by median split)
- Baseline tremor severity as measured by BF-ADL scale (by median split)
- Pre-stimulation tremor power, aggregated over first week (by median split)

Comparisons within subgroups will be performed using the same statistical tests as specified above for the overall cohort.

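### SAP 3.10 cuts at least seven numeric baseline factors in two, tests only within the resulting groups, and plans no analysis of response on the measured scale

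*SAP*

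**What the plan says.** SAP 3.10 lists 12 factors for the primary and secondary endpoints. Nine are numeric, and all nine are cut in two. Seven of these are baseline factors:

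- age, cut at 65;
- age at onset: "Age onset of hand tremor in PD (by median split";
- disease duration: "Duration of PD from beginning of tremor symptom (by median split";
- preset amplitude: "Preset Stimulation amplitude (by median split";
- calibration frequency: "Stimulation calibration frequency (by median split";
- baseline UPDRS: "Baseline tremor severity as measured by UPDRS (by median split";
- baseline BF-ADL, also at the median.

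The other two, average final amplitude and first-week pre-stimulation tremor power, are measured after treatment starts, so I leave them out of the count.

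On testing, the section says only: "Comparisons within subgroups will be performed using the same statistical tests as specified above for the overall cohort". It names no comparison between the two levels, no interaction test, no regression and no correlation. The correlations in SAP 3.9 compare early days with late days, or Visit 2b with Visit 3. They do not relate a subject's response to a baseline factor. Neither document gives a reason for the cuts.

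**The concern.** The section title promises a covariate analysis and none follows. A split treats subjects just either side of the cut as opposites and subjects far apart on the same side as alike. A sample median also depends on who enrols, so a finding above or below it does not carry over directly to another sample. With about 30 to 45 evaluable subjects, there is little information on which patients respond, and splitting discards part of it. What is at stake is a missed or poorly described predictor of response. The primary and secondary conclusions do not depend on this section.

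**Working it through.** **The plan's own figure.** SAP 3.6 states 90% power for the primary endpoint at alpha 0.01, with N = 30 for a 4-week study and 10% attrition. The sample sizes are consistent: 30/0.90 = 33.3, rounded up to 34, and 45/0.90 = 50. The 90% cannot be checked because no effect size is given. Solving back from N = 30 gives a standardised effect of about 0.75 (two-sided) or 0.69 (one-sided). The documents state no power for any subgroup analysis, so there is no planned figure to reproduce on this point.

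**Inputs.**
- Level: two-sided 0.05, from SAP 3.1 ("All hypothesis testing will be performed using a two-sided test at a 0.05 level of significance"), with no multiplicity adjustment.
- Evaluable subjects: 34 to 50 less 10% (SAP 3.6) gives 34 × 0.9 = 30.6, taken as 30, up to 50 × 0.9 = 45. I also ran 50 with no loss.
- Correlation ρ between factor and log kinematic response: not in the documents. Assumed 0.2 to 0.6.
- Assumed normal factor, linear relation, and a test between the two halves. SAP 3.10 does not plan that last test.

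**Step 1: information kept.** The correlation between a normal variable and its above/below-median indicator is √(2/π) = 0.798. Squared, this is 2/π = 0.637, so the split keeps about 64% of the information. 45 × 0.637 = 28.6, so 45 subjects act like about 29.

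**Step 2: power at N = 45.** By Fisher's z, power ≈ Φ(√(N − 3) · atanh(r) − 1.96), with r = ρ for the measured scale and r = 0.798ρ for the split. For ρ = 0.4:
- measured scale: √42 × atanh(0.400) = 6.481 × 0.4236 = 2.746, and Φ(0.786) = 78%;
- split: 6.481 × atanh(0.319) = 6.481 × 0.3307 = 2.143, and Φ(0.183) = 57%.

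Simulation (40,000 runs per setting; Pearson test against a two-group t-test) agrees closely:

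| ρ | Measured scale, Fisher z | Split, Fisher z | Loss, points | Loss by simulation |
|---|---|---|---|---|
| 0.3 | 51.8% | 35.3% | 16.5 | 17.0 |
| 0.4 | 78.4% | 57.3% | 21.1 | 21.1 |
| 0.5 | 94.5% | 78.2% | 16.4 | 14.7 |

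**Step 3: the wider range.** Loss in points by Fisher z:

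| N | ρ 0.2 | 0.3 | 0.4 | 0.5 | 0.6 |
|---|---|---|---|---|---|
| 30 | 5 | 12 | 19 | 22 | 18 |
| 40 | 7 | 15 | 21 | 19 | 10 |
| 45 | 8 | 17 | 21 | 16 | 7 |
| 50 | 9 | 18 | 21 | 14 | 5 |

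The smallest simulated loss is 3.5 points (N = 50, ρ = 0.6), so the overall range is about 4 to 22.

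**Step 4: rank-based tests.** The primary test is Wilcoxon's signed-rank, so a rank-based comparison may be closer to the plan. At N = 45, Spearman against the rank-sum test loses 13, 18 and 14 points for ρ = 0.3, 0.4 and 0.5.

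**Step 5: the age cut.** A fixed cut need not fall at the median. At N = 45 and ρ = 0.4, the simulated loss is about 22 points for a 40:60 split, 26 for 30:70 and 33 for 20:80, against about 21 at 50:50.

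**The case against.** The best defence is that predictors of response are not a study objective, and that pre-specified two-level tables are a legitimate way to show consistency. That stands. It limits the importance of the point, but does not explain why the measured scale is never used.

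Three stronger readings are tempting, and the documents support none of them.

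- A reader might infer that the plan as written has 15 to 21 points less power to find responders. SAP 3.10 plans no comparison between halves, so that power is undefined. The figure describes a comparison that could be added, under assumed conditions. The missing between-level comparison is the more basic gap.
- A reader might infer that these splits are the study's only evidence on who responds. SAP 3.10 also has sex and medication subgroups. SAP 3.9 plans per-task change and responder rates among patients scoring at least 2 before stimulation, and at-home response by within-patient tremor severity. These are limited, but they exist.
- A reader might infer that the UPDRS split will produce many ties. That would follow if the score were the "average of UPDRS ratings from the two assessed action tremor tasks (postural hold and kinetic) relevant to the stimulated upper limb", which moves in coarse steps, in subjects selected for a postural score of at least 2. But SAP 3.4 gives that definition for the secondary endpoint. SAP 3.9 also uses a six-task average, and SAP 3.10 does not say which is split. Ties are possible, not shown.

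The complaint that the cut point depends on who enrols applies to the six median splits, not to age at 65.

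**Conclusion.** The point holds as a low-cost improvement. At least seven numeric baseline factors are reduced to two groups, only within-group tests are planned, and no analysis uses the measured values. If the halves were compared, a median split would cost about 15 to 21 points of power at 45 evaluable subjects for ρ of 0.3 to 0.5, and about 4 to 22 over the wider range. Both ranges rest on a normal factor, a linear relation, a parametric two-sided 0.05 test and correlations that I have assumed. They do not cover the age cut. The UPDRS split is also under-specified, whatever the correlation.

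**What to change.** In SAP 3.10, for age, age at onset, disease duration, preset amplitude, calibration frequency, baseline UPDRS and baseline BF-ADL:

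1. Regress log kinematic response on the continuous factor, one factor at a time. Do the same for the secondary change scores, since the section covers those endpoints too.
2. Report each slope with its 95% CI, using Spearman's correlation for coarse ordinal scores. Label the set exploratory and without multiplicity adjustment, because SAP 3.1 otherwise calls for adjustment where appropriate.
3. Keep the two-group tables as descriptive displays.
4. State which UPDRS score is split (two action-tremor tasks or the six-task average) and which group takes subjects at the median.

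The cost is SAP wording and one simple regression per factor and endpoint on data already collected. The downside is that a slope assumes a roughly monotone relation, which the retained tables and a scatter plot can check. When a change score is related to its own starting value, regression to the mean affects the slope and the two-group table alike, and the text should say so.

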3.3 Primary Endpoint

The primary endpoint (definition below) of the study is a within-subject comparison of tremor power before stimulation to after stimulation, as captured by the Cala Trio device’s on-board accelerometer. Unless otherwise specified, “tremor frequency”, “tremor power” and “single-session kinematic response” are per-session metrics defined as follows:

- “Tremor frequency” is the frequency, in the 3 – 12 Hz range associated with Parkinson’s tremor, where the power spectral density (PSD) of a session’s pre-stimulation accelerometry data is largest.
- “Tremor power” is integral of the PSD of the tremor accelerometry data in the 3 Hz window centered on the session’s tremor frequency.

- “Single-session kinematic response” is defined as the pre-stimulation tremor power divided by the post-stimulation tremor power.

The primary endpoint, “kinematic response”, is defined as the per-patient median of single-session kinematic responses.

Patients will be included in the primary endpoint analysis only if they completed at least 10 therapeutic sessions that met the following data quality criteria:

- Session was started at least 2 hours after the completion of a previous session.
- Participant completed both pre- and post-stimulation motion recordings, that are each
 - sufficiently free of recording artifact, including accelerometer saturation
 - sufficiently free of motion artifact, as detected by excessive power outside the 3 – 12 Hz tremor range in the PSD.

Statistical testing of the primary endpoint will be based on the cohort of all enrolled subjects for whom outcome data are available. The statistical objective related to the primary endpoint is to demonstrate that action hand tremor severity in PD is reduced with the Cala Trio device. Formally, the null and alternative hypotheses to be tested for the primary endpoint is as follows:

$$H_0: M_T \geq 1$$

$$H_A: M_T < 1$$

where M_T is the median kinematic response captured over the 4-week study.

The primary endpoint is a continuous variable and will be summarized descriptively using log-transformed mean and standard deviation, median, and interquartile range (first and third quartiles). Hypothesis testing of the change score M_T will be performed using Wilcoxon’s signed-rank test.

The primary endpoint is met if the two-sided p-value is < 0.05 , such that the null hypothesis is rejected in favor of the alternative hypothesis. The study is successful if the primary endpoint is met.

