The secondary endpoints will be summarized descriptively using mean, standard deviation, median, first and third quartiles, and interquartile range (between first and third quartiles). Hypothesis testing of the mean change score (μ_T) will be performed using one-sample t-tests (equivalent to a two-sample paired test). Formally, the null and alternative hypotheses to be tested for each of the secondary endpoints are as follows:

$$H_0: \mu_T = 0$$

$$H_A: \mu_T \neq 0.$$

Secondary endpoints will only be tested for statistical significance if the primary endpoint is met. Secondary endpoints will be tested in a hierarchical stepwise manner, using a fixed sequence procedure: 1a -1d first, 2a and 2b second, and 3a and 3b third. Statistical significance level will be set at $p < 0.05$ for each of the three endpoint groups, with group 2 (2a, 2b) only tested if all tests in group 1 (1a – 1d) meet significance, and group 3 (3a, 3b) only tested if group 2 meets significance. Because all endpoints within a step (e.g., endpoints 1a – 1d in endpoint group 1) must meet the two-sided $p < 0.05$ in order to proceed to the next step, no adjustment for multiplicity is required.

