3.6 Sample Size and Power

The study sample size (N) is predicated on primary endpoint as detailed above. For the analysis, primary endpoint as well as the secondary endpoints will be tested on the ITT & PP populations. Estimates of effect size for the various outcomes are shown below. Assuming the same effect sizes observed in PROSPECT (clinicaltrials.gov NCT03597100), at $p = 0.01$ we have the following results:

Metric	p value	N
Kinematic measurements for study duration of 2 weeks	0.01	40
Kinematic measurements for study duration of 4 weeks	0.01	30

Under these effect sizes, assuming up to 10% data attrition and with a paired difference test at 0.01 alpha against the null hypothesis of no change from baseline, the 34 to 50 subject analysis provides 90% power for testing of the primary endpoint.

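### SAP 3.10 tests each subgroup level only against no change, so it cannot show whether the effect differs by any of its 12 factors, and no rule stops differing p-values being read that way

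*SAP*

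**What the plan says.** SAP 3.10 opens: "Primary and secondary endpoints will be investigated for each of the following subgroups". It lists 12 factors, each with two levels. Eight are median (or median/mean) splits; sex, age at 65, tremor medication and antidepressant medication have fixed levels. The only method is the closing sentence: "Comparisons within subgroups will be performed using the same statistical tests as specified above for the overall cohort".

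The tests referred to are in SAP 3.3 and 3.4. The primary endpoint, the per-patient median ratio of pre- to post-stimulation tremor power, is tested against 1 "using Wilcoxon’s signed-rank test". Each of the eight secondary change scores is tested against 0 with a one-sample t-test. The primary criterion is: "The primary endpoint is met if the two-sided p-value is < 0.05".

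The section title mentions covariates, but neither document specifies a covariate model, an interaction term, a two-sample test or an interval for a difference between levels. SAP 3.5 and Protocol 9.6 say only that subgroups will be looked into and reported. SAP 3.1 promises multiplicity adjustment where it is appropriate, has p-values reported uncorrected, and gives no subgroup rule.

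**The concern.** A one-sample test inside a level asks whether tremor changed in those subjects. A subgroup analysis asks whether the change differs between levels. Significance in one level and not in the other does not answer that, because each level has fewer subjects than the whole cohort and can miss an effect it shares with the other level.

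The planned output is therefore a table of within-level p-values for sex, age, medication, stimulation amplitude, severity and so on. It contains nothing that measures a difference and no instruction on how to read a split result. What is at stake is the interpretation of that table, not the study's success criterion.

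**Working it through.** **Inputs**
- 12 factors with two levels each (SAP 3.10); two-sided 0.05 (SAP 3.3).
- Base N of 30 for 4-week kinematics, sized "with a paired difference test at 0.01 alpha against the null hypothesis of no change from baseline" (SAP 3.6).
- Stated power: 90% on the primary endpoint for between 34 and 50 subjects (SAP 3.6).
- Attrition up to 10% (SAP 3.6).
- Effect size and SD: not given, so assumed below.

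**1. The plan's own figures.** 30 / 0.90 = 33.3, which rounds up to 34, so the lower end of the range reproduces. 40 / 0.90 = 44.4, which rounds up to 45, so the upper end of 50 is not the inflated 2-week N. N = 30 itself cannot be reproduced without an effect size.

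**2. Assumed effect.** Solving d = (z_alpha + z_power) / √n for n = 30, two-sided 0.01 and 90% power gives (2.576 + 1.282) / 5.477 = 0.70. The exact t calculation gives 0.75. The sidedness of the 0.01 is not stated; one-sided, the normal formula gives 0.66. The back-solving is circular and serves only to obtain a planning value.

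**3. Chance of a split verdict when everyone has the same effect.** Power in a level of size n is P(|T| > t(0.975, n−1)), with T noncentral t, noncentrality d√n. The chance that exactly one level is significant is p1(1 − p2) + p2(1 − p1).

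| N (halves) | d | power per half | exactly one significant | × 12 factors |
|---|---|---|---|---|
| 50 (25/25) | 0.70 | 0.919 | 2 × 0.919 × 0.081 = 0.149 | 1.8 |
| 50 (25/25) | 0.75 | 0.949 | 2 × 0.949 × 0.051 = 0.097 | 1.2 |
| 34 (17/17) | 0.70 | 0.773 | 2 × 0.773 × 0.227 = 0.351 | 4.2 |
| 34 (17/17) | 0.75 | 0.827 | 2 × 0.827 × 0.173 = 0.286 | 3.4 |

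At N = 45 (22/23) the rate is 20% at d = 0.70 and 14% at d = 0.75. At d = 0.66 it is 20% (N = 50) to 40% (N = 34). Simulating the signed-rank test itself at d = 0.70 gives 17%, 22% and 37% at N = 50, 45 and 34. Unequal levels raise the rate: a 30/70 split at d = 0.70 gives 30% (N = 50) to 50% (N = 34).

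Across 12 balanced splits of the same subjects, simulation gives at least one split verdict on the primary endpoint in about 33% (N = 50, d = 0.75) to 71% (N = 34, d = 0.70) of trials.

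**4. Smaller effects.** For assumed d of 0.3 to 0.5 and N of 34 to 50, the same formula gives 34% to 50% per factor, or about 4 to 6 of 12 per endpoint. The documents give no effect sizes for the secondaries.

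**5. Comparator.** With the same effect in everyone, a between-level test at 0.05 gives a false difference in 5% of factors, or 12 × 0.05 = 0.6 expected. Its power is low. The difference detectable with 80% power is (1.96 + 0.84) × √(2/25) = 0.79 SD at 25 per level and 2.80 × √(2/17) = 0.96 SD at 17 per level.

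**6. Exception to the comparator.** SAP 3.9 takes baseline as Visit 2b pre-stimulation. That is the starting value of six of the eight secondaries (1a, 1c, 2a, 2b, 3a, 3b). Change is post minus pre, so measurement error in the pre value appears in both the factor and the outcome. Simulating 45 subjects with an identical effect in everyone, at assumed reliabilities of 0.9 to 0.8, a between-half test was falsely significant in 21% to 40% of trials and a regression on the continuous baseline in 31% to 56%. First-week pre-stimulation tremor power raises the same problem for the primary endpoint, because those readings are numerators of the kinematic response.

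**The case against.** The strongest defence is that the SAP nowhere says a split result means a different effect. That is correct. A reader might infer that the plan will declare the device effective in one half and not in the other, or use the table to decide who is said to benefit. The documents contain no such rule. What remains is an omission: within-level tests are the only inference planned, and nothing says how to read them.

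Three other strong readings are tempting and go too far.

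- **Splits in nearly half of all factors.** That follows from d = 0.5, which is not in the documents. At the effect implied by N = 30 and with 50 subjects, most trials would show no split on the primary endpoint.
- **Many false positives.** A reader might count 12 × 2 × 9 = 216 tests and expect 216 × 0.05 = 10.8 false positives if nothing works. SAP 3.4 tests the secondaries only if the primary is met, with further gates between groups. If that gating carries into subgroups, which the SAP leaves unstated, mostly the 24 primary-endpoint tests remain, with 24 × 0.05 = 1.2 expected.
- **Double that count for two populations.** SAP 3.6 says "primary endpoint as well as the secondary endpoints will be tested on the ITT & PP populations", but SAP 3.10 names no population for subgroups.

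Two defences fail. The descriptive-reporting statement at the end of SAP 3.9 covers the exploratory endpoints listed there, not 3.10, which applies hypothesis tests to the primary and secondary endpoints. Multiplicity adjustment would not help either, because an adjusted one-sample test still does not compare levels.

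**Conclusion.** The point holds as an omission in SAP 3.10. The planned tests cannot show whether the effect differs by any factor, and no rule keeps differing p-values from being taken as a difference. The size depends on an assumed effect. At d of 0.70 to 0.75, uniform across subjects and with balanced splits, a split verdict arises in about 10% to 15% of factors at N = 50 and 29% to 35% at N = 34. For d of 0.3 to 0.5 it is 34% to 50%.

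The consequence is limited to how subgroup findings are interpreted, since success rests on the overall primary endpoint. The change is worth making because it costs little.

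**What to change.** Replace the last sentence of SAP 3.10 with the following.

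- For each factor, report the between-level difference with a 95% confidence interval: a two-sample comparison of log kinematic response for the primary endpoint and of change for the secondaries. For age, age at onset, duration, amplitude and calibration frequency, a regression on the continuous value may be used instead.
- Report the estimate and 95% confidence interval in each level, without within-level p-values.
- Label the section exploratory. State the analysis population, whether the SAP 3.4 gating applies, and either a multiplicity rule or that there is none.
- For factors built from an endpoint's own starting value (baseline UPDRS, baseline BF-ADL, first-week pre-stimulation tremor power), do not test change against that value. Report them descriptively with a regression-to-the-mean caveat, or use severity from a separate occasion, such as the Visit 1 UPDRS already collected.

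The cost is SAP wording and a few lines of code. Data collection and the primary analysis do not change. The downsides are low power (about 0.8 SD is needed for 80% power at 25 against 25), so the interval matters more than its p-value, and fewer nominally significant subgroup statements.
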